9.3.8. Amenorrhea Rate and Sustained Amenorrhea Rate

Determination of amenorrhea will be based on a patient's daily menstruation status as reported in the eDiary. Amenorrhea for at least 56 consecutive days is defined as the lack of bleeding for at least 56 consecutive days after starting randomized study treatment in pivotal phase 3 study until Week 52. Amenorrhea for at least 28 consecutive days is defined as the lack of bleeding for at least 28 consecutive days after starting randomized study treatment in pivotal phase 3 study until Week 104. The study day when amenorrhea begins is defined as the first study day following the last reported day of menstruation. It will be assumed that there is no menstruation on days when menstrual status is not reported in the eDiary.

A summary of amenorrhea for at least 56 consecutive days will be provided by pivotal phase 3 study treatment group based on the following 56-day time intervals from pivotal phase 3 baseline through Day 365: Week 8 (Days 1 through 56), Week 12 (Days 29 through 84), Week 16 (Days 57 through 112), Week 20 (Days 85 through 140), Week 24 (Days 113 through 168), Week 28 (Day 141 through 196), Week 32 (Day 169 through 224), Week 36 (Day 197 through 252), Week 40 (Day 225 through 280), Week 44 (Day 253 through 308), Week 48 (Day 281 through 336), and Week 52 (Day 310 through 365). No analyses of 56-day amenorrhea after

Week 52 will be performed because some eDiary reporting cycles are less than 56 days. A summary of amenorrhea for at least 28 consecutive days intervals from pivotal study baseline through Day 731 will be provided by pivotal phase 3 study treatment group. The number and percentage of patients who are amenorrheic (ie, the amenorrhea rate) in each time interval will be presented. In each time interval, the numerator for the amenorrhea rate is the number of patients who did not bleed during the time interval; the denominator is the number of patients who remained on treatment during the entire time interval.

Sustained amenorrhea through week 52, defined as lack of bleeding for at least 56 days that continues until the Week 52 visit or the date of last dose of extension study treatment for early terminated patients who terminated before Week 52, will be summarized by pivotal phase 3 study treatment group in the time intervals defined above. No analyses of sustained amenorrhea after Week 52 will be performed because some eDiary reporting cycle were less than 56 days. In each time interval, the number and percentage (ie, the sustained amenorrhea rate) of patients with sustained amenorrhea will be presented. In each time interval, the numerator of the sustained amenorrhea rate will be the number of patients with sustained amenorrhea beginning on or prior to the end of the time interval; the denominator will be the number of patients in the Extension Safety population. For patients who discontinued early, their amenorrhea status at the time of discontinuation will be carried forward until Week 104.

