7.2.4. Definitions Related to Numerical Rating Scale Pain Scores and Analgesic Use

Dysmenorrhea NRS Scores

Dysmenorrhea NRS pain scores are pain scores reported in the eDiary on days that the patient reports she is bleeding. Non-menstrual pelvic pain NRS pain scores are those pain scores reported in the eDiary on days that the patient reports she is not bleeding.

Baseline Assessment of NRS Pain Scores and Analgesic Use

Pivotal phase 3 study baseline NRS pain scores will be used as baseline NRS pain scores in the extension study analyses. Baseline NRS pain scores for DYS and NMPP are the averages of the respective eDiary pain scores reported during the baseline pain assessment period.

Pivotal phase 3 study baseline analgesic use for pelvic pain will be used as baseline analgesic use in the extension study analyses. It is the average daily pill count as reported in the eDiary during the pivotal phase 3 study baseline pain assessment period. The baseline average daily pill count will be calculated separately for Tier 1 and Tier 2 analgesics.

Week 52 and Week 104/EOT Assessment of NRS Pain Scores and Analgesic Use

The Week 52 pain scores for DYS and NMPP are the averages of the respective eDiary pain scores reported during the Week 52 pain assessment period (PAP), defined as the last 35 calendar days of extension study treatment immediately prior to Week 52. For patients with extension study treatment duration less than 35 days, Week 52 PAP is defined as the days between the first dose of extension study drug and date of last dose of extension study drug.

Week 52 analgesic use for pelvic pain is the average daily pill count as reported in the eDiary during the Week 52/ PAP. The average daily pill count will be calculated separately for Tier 1 and Tier 2 analgesics for Week 52.

Since eDiary is not required to report out of the eDiary collection cycle, ie. Week 53 - 57, Week 66 - 70, Week 79 - 84 and Week 92 - 97, study days in those periods would not be included in the Week 104/EOT pain assessment period or analgesic use for primary endpoints analyses.

The Week 104/EOT pain scores for DYS and NMPP are the averages of the respective eDiary pain scores reported during the Week 104/EOT PAP, defined as

- If the last 35 calendar days prior to and including date of last dose of extension study drug are entirely within an eDiary collection period, then the PAP will be the last

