9.3.7. Analysis of Bleeding Profiles

Bleeding profile categories will be determined based on the amount of bleeding experienced by patients as reported in the eDiary. When a patient is menstruating, the amount of bleeding during the past 24 hours is captured daily in the eDiary with five response options: spotting, light, moderate, heavy, and extremely heavy. It will be assumed that there is no bleeding on days that the patient either uses the eDiary and reports that she is not menstruating, or when the patient misses reporting menstruating within eDiary cycle. The responses to the eDiary question about the amount of bleeding will be used to define the bleeding profile categories (Table 25).

After Week 52, to reduce patient burden, eDiary data were collected over four eDiary collection cycles on the following schedule: Week 57 to the Week 65 visit, Week 71 to the Week 78 visit, Week 85 to the Week 91 visit, and Week 98 to the Week 104 visit. After the Week 104 visit, patients continued daily eDiary entry until the 30-day Follow-Up visit.

Table 25: Definitions of Bleeding Profile Categories

Bleeding Profile Category	Category Definition
Irregular bleeding	3 to 5 bleeding/spotting episodes and less than 3 bleeding-free intervals of least 14 days during a bleeding-profile period
Prolonged bleeding	Bleeding/spotting episodes of more than 14 days during a bleeding-profile period
Frequent bleeding	More than 5 bleeding/spotting episodes during a bleeding-profile period
Infrequent bleeding	1 or 2 bleeding/spotting episodes during a bleeding-profile period
No bleeding	No bleeding during a bleeding-profile period
Normal bleeding	None of the above definitions are met

^a Bleeding/spotting episode: at least one day with bleeding or spotting reported, bounded by bleeding-free intervals.

^b Bleeding-free interval: at least two consecutive days with no bleeding or spotting reported, bounded by bleeding/spotting episodes.

The number and percentage of patients belonging to each of the bleeding profile categories defined in Table 25 will be summarized by pivotal phase 3 study treatment group over four bleeding-profile periods: Days 1 through 90, Day 91-Day 180, Day 181-Day 270, and Day 271-365. A patient must have at least 90 days of treatment exposure to be included in the summary of each period. No analyses of bleeding profile after Day 365 will be performed because all of the eDiary reporting cycles are less than 90 consecutive days.

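### Section 9.3.8 counts unreported diary days as no menstruation and sets no minimum diary entry, so non-reporting can only raise the amenorrhea rates

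*SAP*

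**What the plan says.** SAP Section 9.3.8 derives amenorrhea from the daily menstruation status in the eDiary. For days with no entry it states: "It will be assumed that there is no menstruation on days when menstrual status is not reported in the eDiary". An amenorrhea spell starts on the day after the last reported day of menstruation.

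For the interval rates, "the denominator is the number of patients who remained on treatment during the entire time interval". For sustained amenorrhea, "the denominator will be the number of patients in the Extension Safety population". Neither denominator depends on diary completion. The section mentions no cross-check against the eCRF and no sensitivity analysis.

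The 56-day intervals are listed one by one and end at Day 365. For the shorter measure the section says only: "A summary of amenorrhea for at least 28 consecutive days intervals from pivotal study baseline through Day 731 will be provided". It does not list those intervals.

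Section 9.3.7 makes the same assumption for the bleeding profiles, but confines it to days "when the patient misses reporting menstruating within eDiary cycle". After Week 52 the diary runs in four cycles with gaps between them. Section 7.2.4 leaves the gaps out of the Week 104/EOT pain and analgesic assessments: "Since eDiary is not required to report out of the eDiary collection cycle".

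On women who stop early, Section 9.3.8 says that "their amenorrhea status at the time of discontinuation will be carried forward until Week 104", although it also says: "No analyses of sustained amenorrhea after Week 52 will be performed".

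**The concern.** A blank diary is not evidence of no bleeding. Under this rule a blank day can turn unknown or actual bleeding into amenorrhea, and it can never do the reverse. A woman on drug who makes no entries in an interval is a success in the interval rate. A woman who makes none in the 56 days before Week 52, or before her last dose if she stopped earlier, is a success in the sustained rate. The reported rates would then partly measure diary non-compliance.

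The SAP is more careful with the same diary elsewhere. For dysmenorrhea with no diary scores, Section 7.2.6 and Table 14 consult the menstruation eCRF. The score is set to zero only if no menstruation is recorded there; otherwise it is treated as missing and imputed. For non-menstrual pelvic pain at least 14 diary days are required. Section 7.2.3 confirms that menstruation status is recorded on a CRF page at each visit, so a second source exists that Section 9.3.8 does not use.

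**Working it through.** The SAP states no amenorrhea rate and no diary-compliance figure, so there is nothing to reproduce. The rates and non-reporting shares below are assumptions, shown as ranges.

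**1. Empty diaries.** Let a be the true amenorrhea rate, taken as equal in women who report and women who do not, and u the share of denominator patients with no entries in the interval.

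- Rate under the SAP rule: a(1 − u) + u = a + u(1 − a)
- Excess: u(1 − a)
- Rate with empty diaries counted as bleeding: a(1 − u)

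| a (assumed) | u (assumed) | SAP rule | Excess (points) | Missing as bleeding |
|---|---|---|---|---|
| 70% | 5% | 71.5% | 1.5 | 66.5% |
| 70% | 10% | 73.0% | 3.0 | 63.0% |
| 70% | 15% | 74.5% | 4.5 | 59.5% |
| 50% | 5% | 52.5% | 2.5 | 47.5% |
| 50% | 10% | 55.0% | 5.0 | 45.0% |
| 50% | 15% | 57.5% | 7.5 | 42.5% |

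**2. Scattered missed days.** If a bleed lasts k days and each day is missed independently with probability p, the SAP rate is a + (1 − a)p^k. Section 7.2.6 gives 3 to 7 bleeding days as typical. With a = 70% and p = 20%:

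- k = 3: 0.70 + 0.30 × 0.008 = 70.2%
- k = 1: 0.70 + 0.30 × 0.20 = 76.0%

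The bias therefore comes from empty or nearly empty diaries and from isolated bleeding days, not from occasional lapses.

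**3. Diary-off weeks.** The Table 3 target days (456, 547, 638, 731) less the Table 11 look-backs (56, 56, 48, 51) give cycle starts at Days 400, 491, 590 and 680.

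| Diary on | Preceding diary-off stretch | Length of stretch | 28-day window in Section 9.3.7 |
|---|---|---|---|
| 400–456 | 366–399 | 34 days | 429–456 |
| 491–547 | 457–490 | 34 days | 520–547 |
| 590–638 | 548–589 | 42 days | 611–638 |
| 680–731 | 639–679 | 41 days | 704–731 |

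All four windows lie wholly inside a cycle. They still do if the cycles start strictly at Weeks 57, 71, 85 and 98 (Days 400, 498, 596 and 687). If Section 9.3.8 instead used back-to-back 28-day intervals from Day 366, 3 of 13 would be wholly diary-off (366–393, 562–589, 646–673) and 6 more partly so. In the three wholly diary-off intervals every treated woman with no entries would count as amenorrheic. The section does not say which set applies.

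**The case against.** Three stronger readings are tempting, and the document does not support them.

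First, a reader might infer that the diary-off weeks inflate the planned results, since each stretch exceeds 28 days and so meets the 28-day definition by itself. The 56-day and sustained rates end at Week 52, while the diary is still daily, so they cannot be affected. The 28-day rate is defined per interval, and no ever-amenorrheic rate is planned. The wording on 28-day intervals through Day 731 closely parallels Section 9.3.7, whose windows contain no diary-off days. Table 11, note g, also restricts the Week 65, 78, 91 and 104 assessments to in-cycle data. What stands is a gap in wording: Section 9.3.8 neither names its windows nor carries the in-cycle limit.

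Second, a reader might infer that the carry-forward to Week 104 inflates later results or contradicts the menstruation-recovery follow-up in Section 9.3.6. It feeds no planned output after Week 52, and it carries non-amenorrhea forward as well. For early terminators sustained amenorrhea runs only to the last dose, while Section 9.3.6 separately summarizes return of menses afterwards. What stands is an internal inconsistency of dates.

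Third, 1.5 to 7.5 points might be read as an estimate. It is an illustration, because the SAP says nothing about diary compliance.

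It can also be said that the rule is openly stated, and that the Introduction claims consistency with the pivotal studies, which a new evaluability rule could disturb. An evaluable-only rate is itself unbiased only if non-reporting is unrelated to bleeding. These points argue for showing the rates side by side. They do not justify leaving a one-directional rule without a check.

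**Conclusion.** The point holds for non-reporting in general: under Section 9.3.8 missing diary data can only raise the amenorrhea and sustained amenorrhea rates, and nothing in the section limits or displays the effect. Its size depends on how many women have empty or nearly empty diaries, which is unknown from the document, and on non-reporters having the same true rate as reporters, which the formula assumes. The diary-off weeks and the carry-forward need clearer wording but are not shown to bias any planned result. Amenorrhea is a descriptive safety summary outside the Table 1 endpoints, so the change is worth making but not critical.

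**What to change.** In Section 9.3.8:

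- State that the 28-day rate uses the windows listed in Section 9.3.7, and limit the no-menstruation assumption to days within an eDiary cycle.
- Prespecify a minimum of diary entries for an interval to be evaluable. As an example, and openly a choice, 80% means at least 23 of 28 days (0.8 × 28 = 22.4) or 45 of 56 days (0.8 × 56 = 44.8).
- Do not count as amenorrheic a woman whose eCRF records menstruation in the interval. This matters because up to 5 missed days (28 − 23) could still hide a short bleed.
- Report the rate among evaluable patients, together with a bound that counts non-evaluable patients as not amenorrheic. The current rule can stay alongside if consistency with the pivotal studies is wanted.
- End the carry-forward at Week 52, since no sustained analysis is done later.

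The cost is SAP wording and a compliance flag. The rates may be slightly lower and some intervals will not be evaluable.

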9.3.6. Menstruation Recovery

Status of menstruation recovery will be documented at the Follow-Up visit. Patients whose menses has not resumed as of the Follow-Up visit for whom there is no explanation for the lack of resumption (eg, medical procedure or medications) will be contacted again by telephone 3 (+0.5) months after the Follow-Up visit to determine if menses has resumed and will be asked about factors that may affect resumption of menses.

Menstruation recovery data will be presented in the table by pivotal phase 3 study treatment group for patients in the Extension Study Population. The table will include menstruation status during follow up, number of days to return of menses from last dose of study drug, and

explanation for the lack of menstruation resumption. Menstruation recovery data will also be provided in a by-patient listing,

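### The rate labelled sustained amenorrhea through Week 52 counts women who stopped drug earlier and were amenorrheic only up to their last dose

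*SAP*

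**What the plan says.** SAP Section 9.3.8 defines sustained amenorrhea through Week 52 as a bleeding-free run lasting 56 days or more, with this end point for the run: "continues until the Week 52 visit or the date of last dose of extension study treatment for early terminated patients who terminated before Week 52". The numerator for each interval is "the number of patients with sustained amenorrhea beginning on or prior to the end of the time interval", and "the denominator will be the number of patients in the Extension Safety population". On what happens after stopping, the section says: "For patients who discontinued early, their amenorrhea status at the time of discontinuation will be carried forward until Week 104". The same paragraph also states: "No analyses of sustained amenorrhea after Week 52 will be performed because some eDiary reporting cycle were less than 56 days".

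The plain amenorrhea rate in the same section works differently. There, "the denominator is the number of patients who remained on treatment during the entire time interval".

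The SAP also plans to observe bleeding after the last dose:
- Section 2.1 keeps the eDiary, including menstrual bleeding, going through the follow-up period of about 30 days.
- Section 3.2 records in the eCRF the onset date of the first menstruation after treatment, if it comes before the Follow-Up visit.
- Section 9.3.6 tabulates "number of days to return of menses from last dose of study drug" and arranges a further telephone contact for women whose menses have not resumed without explanation.

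**The concern.** The label says the amenorrhea lasted through Week 52. For a woman who stopped earlier, the rule only asks that it lasted to her last dose. She then stays in the numerator up to Week 52, in an all-patient denominator, while off drug and in a period when the SAP itself looks for menses to return. One table can show that her menses returned while another counts her as sustained amenorrhea through Week 52.

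The two groups of women also face different tests. A woman on drug is exposed to failure until the Week 52 visit; a woman who stops is exposed only until her last dose. No formal comparisons are planned, so the reported percentage is itself the result, and a reader will take it at its label.

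**Working it through.** **Figures the SAP gives.** There is no planned or expected rate for sustained amenorrhea, and no discontinuation rate, so there is no figure of this kind to reproduce. The only planning number is enrolment in Section 2.2: 0.67 x 1200 = 804, which agrees with the stated approximately 800. It is used below only to turn percentage points into women.

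**Following one woman through the rules.** Suppose amenorrhea begins on Day 100 and the last dose is on Day 200.
- Her run is 200 - 100 + 1 = 101 days, which is at least 56 and reaches her last dose, so she qualifies.
- She enters the cumulative count at Week 16, whose interval ends on Day 112, the first to end on or after Day 100.
- She stays in the count for Weeks 32, 36, 40, 44, 48 and 52, which end on Days 224, 252, 280, 308, 336 and 365, all after her last dose. The last ends 365 - 200 = 165 days after it.
- Bleeding after Day 200 does not change her status.

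Now suppose the same woman stays on drug and bleeds on Day 320. Taking the Week 52 visit as Day 365, the run that remains is 365 - 320 = 45 days. That is under 56, so she is not sustained in any interval.

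**Size of the effect at Week 52.** Let
- d = share of the population stopping before Week 52,
- a = share of those stoppers with at least 56 bleeding-free days at last dose,
- c = share of women still on drug at Week 52 who have sustained amenorrhea.

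Rate under the SAP rule = (1 - d)c + d x a.

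Rate with stoppers counted as not sustained = (1 - d)c.

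Difference = d x a, whatever the value of c.

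The SAP gives none of d, a or c. With assumed ranges for d and a, and 800 women:

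| d | a | d x a | women of 800 |
|---|---|---|---|
| 10% | 50% | 5 points | 40 |
| 10% | 70% | 7 points | 56 |
| 20% | 50% | 10 points | 80 |
| 20% | 70% | 14 points | 112 |
| 30% | 50% | 15 points | 120 |
| 30% | 70% | 21 points | 168 |

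As an illustration, with d = 20% and a = c = 70%, the SAP rule reports 0.80 x 0.70 + 0.20 x 0.70 = 70%. The stricter rule reports 0.80 x 0.70 = 56%.

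**Which words produce the effect.** The last-dose clause in the definition already makes the stopper a success at Week 52. Deleting the carry-forward sentence alone would leave the Week 52 rate unchanged. Changing the definition alone would leave a sentence that can be read as putting her back. Both have to be dealt with.

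**The Week 104 end point.** The paragraph says "No analyses of sustained amenorrhea after Week 52 will be performed", so a sustained status carried to Week 104 feeds no sustained analysis. The 28-day amenorrhea rate does run to Day 731, but it admits only women on treatment for the whole interval, so it has no use for a carried status either.

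**The case against.** The strongest defence is that the SAP states the rule openly. Read in full, the measure is the share of treated women who are in amenorrhea when their on-treatment observation ends, at Week 52 or at last dose. The Week 104/EOT primary endpoint is also anchored at the last dose. Return of menses off drug is reported separately in Section 9.3.6, so it is not hidden, and the carried value is simply status at stopping. On this view, counting stoppers as failures is a different choice rather than a correction. That stands as far as it goes: a measure to Week 52 or last dose is legitimate. The label of this one says something else.

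Four further points on that side also stand.
- The 56-day amenorrhea rate for Days 310 through 365, among women on treatment throughout, is already planned in Section 9.3.8. An on-treatment companion rate need not be added.
- The intervals cumulate women by onset of sustained amenorrhea; they do not show who is amenorrheic in each period. Swapping in a changing on-treatment denominator would spoil that display.
- The size given above rests on assumed inputs and on one particular comparator.
- The measure is descriptive and does not appear among the endpoints in Table 1.

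A reader might go further and infer that dropout can never lower the reported rate. The document does not support that. Women who stop while bleeding, or with fewer than 56 bleeding-free days, stay in the denominator as failures. With d = 20%, c = 70% and a = 50%, the SAP rate is 0.80 x 0.70 + 0.20 x 0.50 = 66%, below the 70% among women still on drug. The accurate statement is narrower: a woman who qualifies at her last dose can no longer become a failure.

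**Conclusion.** The mismatch between label and count is real. The rate presented as sustained amenorrhea through Week 52 includes women off drug before Week 52 whose amenorrhea is known only to their last dose, and it keeps them even where the trial has recorded that menses returned. Against a rule that counts stoppers as not sustained, the excess is exactly d x a: 5 to 21 points if 10-30% stop before Week 52 and 50-70% of them qualify. Those shares are assumptions, and the SAP offers nothing to narrow them.

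Two stronger readings should not be drawn. The carry-forward to Week 104 does not distort any Week 104 result, because no planned analysis uses it; it is an internal inconsistency. And no error rate is affected, because the SAP plans no formal comparisons. Severity is minor to moderate.

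**What to change.** In Section 9.3.8, change both the last-dose clause in the definition and the carry-forward sentence, so that the all-patient rate through Week 52 counts women who stopped before Week 52 as not sustained. Keep the Extension Safety population as denominator.

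If the sponsor wants to keep the current measure, relabel it as sustained amenorrhea to Week 52 or last dose, show how many early stoppers are in its numerator, and present it beside the stricter rate.

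In either case, remove the reference to Week 104, since sustained amenorrhea is not analysed after Week 52.

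The cost is some SAP wording and one revised table, from data already collected. The drawback for the sponsor is a less favourable all-patient rate.
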